Design and methodology	
It is open-label safety, tolerance and pharmacokinetics study with intra-cohortal randomization of PBTZ169, capsules 40 mg in healthy volunteers after single and multiple oral administrations. The study includes two stages:
 
 • - Stage 1 - single dosing with dose escalation • - Stage 2 - multiple dosing with dose escalation. 
Stage 1 (single dosing with dose escalation)
 
Totally, 5 cohorts (C1-C5) are planned to be enrolled during the first stage of the study with 7 subjects in each (6 volunteers and 1 back-up) to investigate the drug after single administration. Screening procedures to include volunteers into each cohort will be performed within 7 days before the drug prescription.
 
Healthy volunteers complying with the study inclusion criteria, will be admitted to hospital in the evening before the test drug administration and randomized into the main group and back-up group.
 
Healthy volunteers complying with the study inclusion criteria will be included successively into the following cohorts:
 
 • Cohort 1 (C1) includes 6 healthy volunteers of the main group each of whom received a single dose of the drug - 1 capsule containing 40 mg of PBTZ169 and 1 healthy back-up volunteer. • Cohort 2 (C2) includes 6 healthy volunteers of the main group each of whom received a single 80 mg dose of PBTZ169 (2 capsules 40 mg) and 1 healthy back-up volunteer.

- Cohort 3 (C3) includes 6 healthy volunteers of the main group each of whom received a single 160 mg dose of PBTZ169 (4 capsules 40 mg) and 1 healthy back-up volunteer.
- Cohort 4 (C4) includes 6 healthy volunteers of the main group each of whom received a single 320 mg dose of PBTZ169 (8 capsules 40 mg) and 1 healthy back-up volunteer.
- Cohort 5 (C5) includes 6 healthy volunteers of the main group each of whom received a single 640 mg dose of PBTZ169 (16 capsules 40 mg) and 1 healthy back-up volunteer.

In Cohort 1, initially 3 volunteers from the main group will receive the drug simultaneously and the rest 3 volunteers will receive the drug 24 h after it will be have been taken by previous volunteers. In the successive Cohorts, all 6 volunteers of the main group will receive the drug simultaneously.

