Before the volunteers will be included into Cohort 2, the drug pharmacokinetic results will have been received for Cohort 1. Time points for blood and urine sampling can be adjusted for all successive cohorts based on the data concerning pharmacokinetics and safety of administration of PBTZ169 capsules 40 mg.

Screening of volunteers into each successive cohort can be started not earlier than 24 h after all the volunteers from the previous cohort have received the drug. The subjects will be randomized within the cohort after volunteers from previous cohort have received the drug. The volunteers of each successive cohort will administer single dose of the drug minimum 7 days after the volunteers from the previous cohort have received the drug if dose-limited toxicity (DLT) is found in less than 50% volunteers from the group. For Cohort 1, DLT reported in 2 volunteers from the first three patients will be considered as achievement of this criterion and will result in the study termination, thus, the successive three subjects will not be included into the study. In this study, DLT will include any class 3 and more toxicity according to Toxicity Grading Scale for Healthy Adult and Adolescent Volunteers Enrolled in Preventive Vaccine Clinical Trials which is "possibly", "probably" and "definitely" related with the administration of PBTZ169.

The volunteers from each group will be admitted to hospital in the evening before dosing.

Back-ups from cohorts C1-C5 will be admitted to hospital simultaneously with the main volunteers of the cohorts for not more than 24 h and will be discharged and complete the study participation

if their participation is not necessary. If back-up is necessary in any cohort, the period of hospitalization and all the study procedures for respective back-up will be equivalent to those for substituted volunteer. In Cohort 1, back-up will be hospitalized with the second three volunteers.

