Each healthy volunteer from the main groups of cohorts C1-C5 will receive only one dose of the test drug in the morning under fasting conditions (10 h of night fasting) with 300 mL of bottled water. On the day of administration, water intake is ad libitum, except for 1 h within the drug administration during which water intake is prohibited and for 4 h after the drug administration (water intake is prohibited during the first hour, water intake will be limited by 100 mL of bottled water ever hour for the successive 3 h). Food intake will be prohibited for 4 h after the drug administration.

Volunteers from cohorts C1 and C2 will have their venous blood samples taken to determine PBTZ169 concentration before the drug administration: -5 min, 0 min, afterwards at the following time points after the drug administration: in 0:10, 0:20, 0:30, 0:45, 1:00, 1:30, 2:00, 2:30, 3:00, 3:30, 4:00, 5:00, 6:00, 8:00, 10:00, 12:00 and 24:00 (h:min).

Volunteers from Cohort 3 will have their venous blood samples taken to determine PBTZ169 concentration before the drug administration: -5 min, 0 min, afterwards at the following time points after the drug administration: in 0:10, 0:20, 0:30, 0:45, 1:00, 1:30, 2:00, 2:30, 3:00, 3:30, 4:00, 5:00, 6:00, 8:00, 10:00, 12:00, 48:00 (h:min).

Volunteers from Cohort 4 will have their venous blood samples taken to determine PBTZ169 concentration before the drug administration: -5 min, 0 min, afterwards at the following time points after the drug administration: in 0:10, 0:20, 0:30, 0:45, 1:00, 1:30, 2:00, 3:00, 4:00, 5:00, 6:00, 8:00, 10:00, 12:00, 24:00 and 48:00 (h:min).

Volunteers from Cohort 5 will have their venous blood samples taken to determine PBTZ169 concentration before the drug administration: -5 min, 0 min, afterwards at the following time points after the drug administration: in 0:10, 0:20, 0:30, 0:45, 1:00, 1:30, 2:00, 3:00, 4:00, 5:00, 6:00, 8:00, 10:00, 12:00, 24:00, 48:00 and 72:00 (h:min).

At every time point of blood sampling for PBTZ169 concentration determination, additional venous blood will be also sampled for further storage of samples for possible determination of additional parameters. Additional blood can be sampled to control the current parameters to assure safety of volunteers.

Urine will be sampled from every volunteer in each of cohorts during the first 24 hours after dosing within the the following time

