administered. Nonclinical investigation of acute toxicity of finished dosage form was performed in rats after intragastric administration of the drug at API doses of 9-360 mg/kg and on rabbits at API doses of 8-32 mg/kg. No fatal cases, gender distinctions and differences from the control groups were reported. Calculation of human equivalent dose (HED) based on NOAED Calculation factor 6 was used for calculation of HED in rats and calculation factor 3.2 was used for that in rabbits. HED calculated based on NOAED in rats for 30 mg/kg [180 (mg/kg)/6]. HED calculated based on NOAED in rabbits for 10 mg/kg [32 (mg/kg)/3.2]. Selection of the most suitable animal species for HED determination In toxicity evaluation experiments in rats and rabbits, the test drug had no effect on the appearance, general condition, physiological parameters, did not affect negatively hematological and biochemical blood parameters and vital signs; did not cause pathomorphological changes. Thus, taking into consideration that use of the lowest HED assures the safest initial human dose, the most suitable species is rabbits (calculated HED is 10 mg/h). Use of safety coefficient, determination of MRID Standard safety coefficient 10 is used in the calculation of MRID. MRID is 1 mg/kg [10 (mg/kg)/10]. Determination of pharmacologically active dose (PAD) Anti-tuberculosis activity of the drug substance was determined on experimental model of acute and chronic tuberculosis in mice and in experimental chronic tuberculosis in guinea pigs. In the experiments, PAD in mice was 25 mg/kg. HED calculated using PAD in mice was 2.08 mg/kg [25 (mg/kg)/12.0]. In the experiments, PAD in guinea pigs was 80 mg/kg. HED calculated using PAD in guinea pigs was 17.02 mg/kg [80 (mg/kg)/4.7]. Thus, HED calculated on the basis of substance activity study varies between 2.08 and 17.02 mg/kg. Taking into consideration that HED calculated using PAD value higher than MRID, initial dose (dose for Cohort 1) will be 1 mg/kg (for subject with 70 kg of body weight complies with 70 mg dose). As volunteers with body weight less than 70 kg can

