	
participate in the study, taking into consideration that PBTZ169 is a novel drug and that the test drug has been manufactured at dose of 40 mg, 40 mg dose will be administered as an initial dose.
 
Maximum dose for this study will be 640 mg as a single dose. Maximum dose can be selected on the basis of lack of negative drug effects when administered at API doses up to 180 mg/kg (HED=30 mg/kg, calculated for a human of 70 kg in body weight - 2100 mg) in rats in subchronic toxicity study, up to 360 mg/kg (HED=60 mg/kg, calculated for a human of 70 kg in body weight - 4200 mg) in rats in acute toxicity study. Thus, selected maximum dose 640 mg is within the range of investigated doses in animals (rats) up to 2100-4200 mg.
 
Dose selection and period of administration for multiple dosing
 
Doses of PBTZ169 for multiple administration will be defined taking into account the results of the data analysis upon study completion by the volunteers from Cohorts 1 to 5, and the conclusions of the independent Committee for data evaluation and study subjects' safety. Two different doses are expected to be chosen for multiple dosing. Good tolerance and safety of the corresponding single dose of the drug will be the defining criteria, including also a determination of a dose-limiting toxicity (DLT) in less than 50% of the volunteers from the respective cohort with single dosing. Presumably, two highest doses among those studied in single administration will be selected, on the condition of a good tolerance of the drug.
 
Multiple administration of PBTZ169 will be performed at hospital under thorough monitoring of volunteers.
 
Taking into consideration that the drug administration period in rabbits and rats was 30 days in the subchronic toxicity study and 180 days in the chronic toxicity study, according to Guidelines for drug evaluation, 2013 (volume I), 14-day period of the test drug administration in this clinical study is justified.

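### Cohorts 4 and 5 (320 and 640 mg) dose all six volunteers at once; keeping Cohort 1's 3 + 3 split there is a cheap safeguard with a small expected gain

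*Combined protocol and SAP*

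**What the plan says.** All references are to section 1, Study Summary.

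- **Cohort 1 dosing** (Design and methodology, Stage 1): "In Cohort 1, initially 3 volunteers from the main group will receive the drug simultaneously". The second half of the cohort is dosed one day (24 h) later, and the back-up is admitted with that second half.
- **Cohort 1 stop:** "For Cohort 1, DLT reported in 2 volunteers from the first three patients will be considered as achievement of this criterion". When it is met, the study ends and the other three are not included.
- **Cohorts 2 to 5 dosing:** "In the successive Cohorts, all 6 volunteers of the main group will receive the drug simultaneously".
- **Between cohorts:** the next cohort is dosed at least 7 days later, and only if fewer than 50% of the group had a DLT. A DLT is a toxicity of class 3 or above that is at least possibly related to the drug.
- **After Stage 1:** an independent committee reviews the data, and the sponsor then sets the Stage 2 doses. Among the conditions for a Stage 2 dose is good tolerance, "including also a determination of a dose-limiting toxicity (DLT) in less than 50% of the volunteers from the respective cohort with single dosing".
- **Dose justification:** the starting dose rests on rabbits ("HED calculated based on NOAED in rabbits for 10 mg/kg"). The maximum dose rests on rats: "Thus, selected maximum dose 640 mg is within the range of investigated doses in animals (rats) up to 2100-4200 mg".

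**The concern.** The less-than-50% rule, the 7-day gap and the committee all act after a cohort has been fully dosed. They protect the next cohort or Stage 2, not volunteers who have already taken the capsules. If 320 or 640 mg is poorly tolerated, six healthy volunteers are exposed before any stated rule can act, and the most recent human data come from half that dose. Cohort 5 has no later Stage 1 cohort, so its DLT result can affect only the choice of Stage 2 doses.

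Clear toxicity at these doses is not excluded by earlier cohorts having passed. The rule allows a doubling after 2 DLTs in six. If the true DLT rate at 320 mg were 30%, the cohort would still pass with probability 0.744; at 50%, with probability 0.344.

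The sponsor already has a suitable procedure in Cohort 1. The question is whether repeating it at the two highest doses is worth the cost.

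**Working it through.** **The plan's own figures.** Stage 1 includes 5 × (6 + 1) = 35 volunteers, as stated. The Cohort 1 stop agrees with the 50% criterion: 2/3 = 67% fails it and 1/3 = 33% passes. The plan states no DLT rate, onset time or operating characteristic for either rule, so the rates p below are assumptions.

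**Probability that the stop fires.** As planned, the number spared by a same-cohort DLT is 0 at every p. With the split, P(fires) = 3q²(1 − q) + q³, where q is the chance that a volunteer has a DLT recognised before the second dosing. Take q = p (all recognised) and q = p/2 (half recognised). The second case matters because sampling runs to 48 h in Cohort 4 and 72 h in Cohort 5, so later events are possible.

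**Expected DLTs.** The plan gives 6p. The split avoids 3p × P(fires).

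| p | P(fires), all | P(fires), half | DLTs as planned | Avoided, all | Avoided, half |
|---|---|---|---|---|---|
| 20% | 0.104 | 0.028 | 1.20 | 0.6 × 0.104 = 0.06 | 0.6 × 0.028 = 0.02 |
| 30% | 0.216 | 0.061 | 1.80 | 0.9 × 0.216 = 0.19 | 0.9 × 0.061 = 0.05 |
| 50% | 0.500 | 0.156 | 3.00 | 1.5 × 0.500 = 0.75 | 1.5 × 0.156 = 0.23 |

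At p = 10%, P(fires) is 0.028 (all) or 0.007 (half), and fewer than 0.01 DLTs are avoided in either case.

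**How much stricter the rule becomes (all recognised).** As planned, a cohort passes with at most 2 DLTs in six. The split also fails a cohort with 2 in the first three and 0 in the last three, which has probability 3p²(1 − p)⁴.

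| p | P(pass), plan | Subtract | P(pass), split | Share of stops that would have ended at 2 of 6 |
|---|---|---|---|---|
| 10% | 0.984 | 0.020 | 0.964 | 0.0197/0.028 = 70% |
| 20% | 0.901 | 0.049 | 0.852 | 0.0492/0.104 = 47% |
| 30% | 0.744 | 0.065 | 0.679 | 0.0648/0.216 = 30% |

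**Margins to the animal no-effect doses, at 70 kg.** Rabbit: 10 mg/kg × 70 = 700 mg, so 700/320 = 2.2-fold and 700/640 = 1.1-fold. Rat, 30-day: 2100/320 = 6.6-fold and 2100/640 = 3.3-fold. Rat, acute: 4200/320 = 13.1-fold and 4200/640 = 6.6-fold.

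**The case against.** The strongest case against is that the plan's choice is coherent. The split sits at first human exposure. Each later step is a single doubling after six volunteers, at least 7 days and a DLT check, with inpatient monitoring to 48 h in Cohort 4 and 72 h in Cohort 5. Extending the split is a preference, and the expected gain at low DLT rates is close to nil. This stands, and it is why the point is an improvement and not a correction.

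Three practical objections also stand:

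- **Timing.** If volunteers 4 to 6 are dosed at 24 h, laboratory results from blood drawn at 24 h cannot be in hand. The review can use only what is available by then, unless dosing waits.
- **Strictness.** At low DLT rates, many stops would fall on cohorts that the plan would have passed.
- **Scope.** The case is made for 320 and 640 mg. Nothing here argues separately for Cohorts 2 and 3.

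A reader might infer from the 1.1-fold rabbit margin that 640 mg is known to be unsafe. The documents do not support that. The rabbit no-effect dose (32 mg/kg) was the highest rabbit dose in the 30-day study, so it marks the edge of exposure tested under daily dosing, not a toxic level, and Stage 1 gives one dose. The plan's rat basis gives 3.3- to 6.6-fold. Nor is it an error that escalation goes above the maximum recommended initial dose, which limits only the start.

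**Conclusion.** The point holds as a cheap improvement limited to Cohorts 4 and 5. In the study summary, no rule can spare anyone within those cohorts once dosing starts. A reader might go further and call the simultaneous dosing a mistake or an inconsistency. The text does not show that, since the split is assigned to Cohort 1 on purpose and the later rules are consistent with it.

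The benefit is material only if a dose is clearly toxic. At a 50% DLT rate, 0.75 DLTs are avoided per cohort with full recognition before the second dosing, and 0.23 with half. At 20% the figures are 0.06 and 0.02. They rest on assumed DLT rates, independent outcomes between volunteers, and the assumed share of DLTs recognised in time. The case for acting is that these are healthy volunteers and the procedure already exists in the plan.

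**What to change.** In Cohorts 4 and 5:

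- Dose three volunteers, then the other three at least 24 h later, and admit the back-up with the second three as in Cohort 1.
- Before the second dosing, document a review of the DLT data then available: adverse events, vital signs, ECG, and safety bloods drawn early enough to be reported. The plan already permits such sampling: "Additional blood can be sampled to control the current parameters to assure safety of volunteers".
- If 2 or more of the first three have a DLT, do not dose the rest. Stop that cohort and further escalation, not the whole study, and treat the less-than-50% criterion as not met.
- State how the rule is read if one of the first three withdraws, since the only back-up comes with the second three.

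**Cost.** About one extra dosing day per cohort, or possibly two if 24 h laboratory results are awaited, and no extra volunteers. When the stop fires, PK data from three volunteers are lost. The chance of passing falls as tabulated above. At 640 mg, failing means that the dose does not meet the DLT condition for Stage 2. The sponsor should accept that stricter standard knowingly.

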periods: 0–2, 2–6, 6–12 and 12–24 h to evaluate pharmacokinetics. 12–24 h urine samples will be analyzed only at non-zero concentration of PBTZ169 in 6–12 h sample.

During the whole period of blood sampling for pharmacokinetics after the drug administration, the volunteers will be at hospital and will be discharged after all procedures planned in the protocol have been finished, afterwards the monitoring will be continued under out-patient conditions.

Thus, total in-patient period for every cohort will be as follows:

- C1 and C2 - 3 days (including the admission day, day of the test drug administration and 24 h after the drug administration)
- C3 and C4 - 4 days (including the admission day, day of the test drug administration and 48 h after the drug administration)
- C5 - 5 days (including the admission day, day of the test drug administration and 72 h after the test drug administration).

After the discharge from hospital, volunteers from C1–C5 should visit the study center in 5±1 days after the drug administration for follow-up procedures (safety evaluation).

14±1 days after the drug administration, the last visit (Visit 3) will take place in the form of phone contact after which the volunteers will finish the study participation. Thus, total follow-up period will be 14 days after the drug administration for each volunteer.

After the last volunteer from those enrolled in the cohorts of Stage 1 completes the study, safety and pharmacokinetics will be analyzed using the data of all cohorts of a single dose study. Upon the termination of an analysis of the data obtained during the Stage I, an independent Committee for data evaluation and study subjects' safety will be called. The results of the session of the Committee dedicated to the discussion of the data obtained in the first 5 cohorts (the results of the statistical analysis) will serve for preparing a resolution about the safety, tolerance and pharmacokinetics of the drug taken once in the first 5 cohorts. Takin into account the resolution of the independent Committee about the data evaluation and the safety of study subjects, the Sponsor will:

- *Determine the doses of PBTZ-169 for multiple administration during the Stage 2 of the study;*
- *Take the decision on the necessity to adjust blood and urine sampling timepoints ;*
- *Take the decision about the necessity of a study procedure correction.*

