Before and after the administration of the first, 7th and last (14th) dose of the test drug, venous blood will be taken from the volunteers to determine PBTZ169 concentration at the following time points: before the first drug dose administration: 0 min (before the drug administration) and for 24 h after the administration of the first, 7th and last (14th) dose of the test drug in: 0:15, 0:30, 0:45, 1:00, 1:30, 2:00, 3:00, 4:00, 6:00, 8:00, 10:00, 12:00, 24:00 (h:min after the drug dosing). 24 h point after the administration of 1 and 7 drug doses should be taken before the successive doses. During drug administration days 3-6 and 9-13, venous blood will be daily taken at 0 min time point (before the drug administration) to determine PBTZ169 concentration. Blood will be sampled at 48 h and 72 h time points after the administration of the last (14) drug dose.

The deviations from the specified time by 10 min to one or another side (\pm 10 min) are acceptable for the following time points: 24 hours for administration of the first, 7th and last (14th) doses of the test drug. For 48 h and 72 h time points after the last (14th) dose administration, deviation from the specified time by 20 min to one or another side (\pm 20 min) is acceptable. For the rest time points, blood sampling after the test drug administration can deviate by not more than 2 min to one or another side (\pm 20 min).

In case of preterm withdrawal from the study, if there is no risk for a volunteers, attempts to sample their blood according to schedule for the last (14) dose will be taken.

At every time point of blood sampling for PBTZ169

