Dose and administration route	
Single oral:
 
 • Cohort 1 — 40 mg • Cohort 2 — 80 mg • Cohort 3 — 160 mg • Cohort 4 — 320 mg • Cohort 5 — 640 mg 
Multiple oral
 
 • Cohort 6 — X* mg/day • Cohort 7 — Y* mg/day 
*The dose of PBTZ-169 will be defined taking into account the results of the data analysis and the conclusions of the independent Committee for data evaluation and study subjects' safety.

Administration period	Single administration in the morning at a fasting state for volunteers from cohorts C1-C5. For volunteers from cohorts C6-C7: daily drug administration o.d. in the morning at a fasting state at the same time±15 min for 14 days.
Reference drug	Not applicable.
Respective therapy	Not applicable.
Primary and secondary variables	
Safety and tolerance variables evaluated
 
 • Adverse events • Changes in vital signs • Results of laboratory analyses (complete blood count, blood biochemistry, urinalysis) • Results of ECG • Results of physical examination 
Pharmacokinetic parameters evaluated (single dosing)
 
 • Maximum concentration (C_{max}) • Time to maximum concentration (T_{max}) • Area under the concentration-time curve from 0 to last blood sampling (t) (AUC_{0-t}) • Area under the concentration-time curve from zero to infinity ($AUC_{0-\infty}$) • Ratio AUC_{0-t} to $AUC_{0-\infty}$ ($AUC_{0-t}/AUC_{0-\infty}$) • Total clearance (Cl) • Renal clearance (Cl_{ren}) • Distribution volume (V_d) • Half-life ($T_{1/2}$) • Mean retention time (MRT) • Absorption rate (C_{max}/AUC_{0-t})

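### Cohort 3 (160 mg) is the only cohort with no 24 h blood sample; the resulting 12–48 h gap can bias or truncate its AUC

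*Combined protocol and SAP*

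**What the plan says.** All references are to the combined protocol and SAP, section 1 Study Summary.

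- **Design and methodology, Stage 1 blood sampling.** The Cohort 3 list ends "3:30, 4:00, 5:00, 6:00, 8:00, 10:00, 12:00, 48:00 (h:min". The Cohort 4 list ends "8:00, 10:00, 12:00, 24:00 and 48:00 (h:min". Cohorts 1 and 2 stop at 24 h; Cohort 5 has 24, 48 and 72 h.
- **Stage 2 blood sampling.** Cohorts 6 and 7 are sampled at 24 h after doses 1, 7 and 14. For the first two of these the text adds: "24 h point after the administration of 1 and 7 drug doses should be taken before the successive doses".
- **Urine.** Every Stage 1 cohort has urine collected in "periods: 0–2, 2–6, 6–12 and 12–24 h to evaluate pharmacokinetics".
- **In-patient stay.** "C3 and C4 - 4 days (including the admission day, day of the test drug administration and 48 h after the drug administration".
- **Changes to the schedule.** "Time points for blood and urine sampling can be adjusted for all successive cohorts", on the basis of pharmacokinetic and safety data.
- **Primary and secondary variables.** AUC0-t runs "from 0 to last blood sampling (t". AUC0-∞, the ratio of the two, half-life, total and renal clearance and distribution volume are also listed.
- **Statistical methods.** The software is named (WinNonlin). The trapezoid rule and the handling of values below the assay limit are not stated.

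**The concern.** The list is the instruction to the site. A site that follows it takes no 24 h sample from Cohort 3, the middle of the five single doses.

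Three features suggest an omission rather than a decision. Cohort 3 shares its 48 h stay with Cohort 4, so the volunteers are present at 24 h. Its urine is collected to 24 h, so a plasma value there has a use. It keeps the dense early grid of Cohorts 1 and 2 (including 2:30 and 3:30), so the schedule was not thinned overall.

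At stake are Cohort 3's AUC0-t and AUC0-∞ and the parameters derived from them, and its comparability with the other doses. AUC0-t ends at 24, 24, 48, 48 and 72 h in Cohorts 1 to 5, so it is not a common yardstick. With a 24 h sample in Cohort 3, the 0–24 h window would be sampled to its end in every cohort. Without it, the longest such window is 0–12 h.

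**Working it through.** **Step 1: the lists side by side** (times after dosing)

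| Cohort | Late samples (h) | 24 h? | Longest gap |
|---|---|---|---|
| 1, 2 | 10, 12, 24 | yes | 12 h |
| 3 | 10, 12, 48 | **no** | **36 h** |
| 4 | 10, 12, 24, 48 | yes | 24 h |
| 5 | 10, 12, 24, 48, 72 | yes | 24 h |
| 6, 7 | 10, 12, 24 (48 and 72 after dose 14) | yes | – |

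The 24 h sample is present in six of seven cohorts. Adding it to Cohort 3 cuts the gap from 48 − 12 = 36 h to 48 − 24 = 24 h.

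**Step 2: assumptions.** The documents give no half-life, absorption rate, assay limit or trapezoid rule, and there is no figure of the plan's own to reproduce. I assume a one-compartment oral model with ka = 1.5/h and k = ln 2 / T½, scaled so that F·Dose/V = 1: C(t) = ka/(ka − k) · (e^(−kt) − e^(−ka·t)). Then AUC0-∞ = 1/k.

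**Step 3: linear trapezoid, 48 h measurable.** Worked for T½ = 6 h: C(12) = 0.2709, C(24) = 0.0677, C(48) = 0.0042. The exact AUC0-48 is 8.620, of which 6.312 lies in 0–12 h and 2.308 in 12–48 h. The grid reproduces the 0–12 h part.

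- Without 24 h: 12–48 h = 36/2 × (0.2709 + 0.0042) = 4.952. Total 11.264; 11.264/8.620 = 1.307, or +31%.
- With 24 h: 12/2 × (0.2709 + 0.0677) + 24/2 × (0.0677 + 0.0042) = 2.895. Total 9.207; 9.207/8.620 = 1.068, or +7%.

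| T½ (h) | 6 | 8 | 12 | 24 |
|---|---|---|---|---|
| AUC0-48 error without 24 h | +31% | +26% | +16% | +5.5% |
| with 24 h | +7% | +6% | +4% | +1.6% |

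**Step 4: log-down trapezoid, 48 h measurable.** For mono-exponential decline the error is about 0% either way. For bi-exponential decline (fast T½ 2–4 h, terminal T½ 12–24 h, slow fraction 10–20%), AUC0-48 is overstated by about 2% to 9% without 24 h and by about 0.5% to 1.7% with it.

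**Step 5: 48 h not quantifiable.** The last usable Cohort 3 sample is then at 12 h. Once absorption is over, the share of AUC0-∞ beyond time t is [C(t)/k] / (1/k) = C(t). At T½ = 6 h this is 27% beyond 12 h and 7% beyond 24 h.

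| T½ (h) | 4 | 6 | 8 |
|---|---|---|---|
| Share beyond 12 h | 14% | 27% | 38% |
| Share beyond 24 h | 2% | 7% | 13% |

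For Cohort 3 to lose its 48 h value while Cohort 1 is still measurable at 24 h (a quarter of the dose, proportionality assumed), the assay limit must lie between C(48) and C(24)/4 of Cohort 3. At T½ = 6 h, C(48) and C(24) are 0.52% and 8.39% of Cmax, so the range is 0.5% to 8.39/4 = 2.1% of Cmax. At 4 h it is 0.04% to 0.6%; at 8 h, 2.0% to 4.0%; at 12 h the range is empty.

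**Step 6: half-life.** Three-point log-linear fits, 10% log-normal noise, true T½ 6 h. If 48 h is unquantifiable, the 90% range is 4.0–12.0 h from 8/10/12 h, against 5.3–6.9 h from 10/12/24 h. If 48 h is measurable and decline is mono-exponential, it is about 5.7–6.3 h either way.

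**Step 7: renal clearance over 0–24 h** (amount in urine divided by AUC0-24), T½ = 6 h. Linear interpolation gives C(24) = 0.2709 − (0.2709 − 0.0042) × 12/36 = 0.1820. AUC0-24 is then 6.312 + 6 × (0.2709 + 0.1820) = 9.029. With a real 24 h value it is 6.312 + 6 × (0.2709 + 0.0677) = 8.343; the exact value is 8.070. Clearance is low by 1 − 8.070/9.029 = 10.6% against the truth, of which 1 − 8.343/9.029 = 7.6% is due to the missing sample. The rest is ordinary linear-rule error. Over 0–12 h there is no effect.

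**The case against.** - **It may be clerical, or deliberate.** Cohort 3 has 17 post-dose samples, the same as Cohorts 1 and 2, which would fit 48 h replacing 24 h at a constant number of draws. The list lacks the conjunction that closes the other Stage 1 lists, which would fit a dropped item; this is weak evidence, since the Stage 2 list lacks it too. The plan also lets sampling times change between cohorts. Intent therefore cannot be settled from the text. Either way, the written instruction contains no 24 h sample and gives no reason.
- **No planned analysis compares cohorts.** The statistical section promises individual curves and descriptive statistics, and no AUC0-24 endpoint or dose-proportionality test is listed. This stands, and it limits the consequence. But AUC0-t, AUC0-∞ and half-life are named outputs in their own right, and the pooled Stage 1 pharmacokinetics go to the independent Committee.
- **The large figures are conditional.** This also stands. The 31% and 26% figures need the linear rule and a measurable 48 h value, which at those half-lives is only 0.5% and 2.0% of Cmax. The truncation figures apply when that value is not measurable, so the two are alternatives and cannot be added. The truncation figures are shares left to extrapolation, not bias in AUC0-∞. The 38% case in step 5 needs an assay limit of 2–4% of Cohort 3's Cmax, hence 8–16% of Cohort 1's (four times as much), which would be an insensitive assay.
- **Stage 2 dose choice barely depends on it.** Tolerance is the stated criterion, and the text expects: "Presumably, two highest doses among those studied in single administration will be selected, on the condition of a good tolerance of the drug". The 160 mg pharmacokinetics matter mainly if those doses are not tolerated.

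**Conclusion.** The concern holds. Cohort 3 alone has no 24 h sample, the documents do not explain it, and following the list loses a point that cannot be recovered. The consequence is that its AUC *can* be biased or truncated. It is not certain to be.

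Under the assumed model the effect runs from about nil (log-down rule, mono-exponential decline, measurable 48 h value) to a 31% overstatement of AUC0-48 (linear rule, T½ 6 h). If 48 h is unquantifiable, 14–38% of AUC0-∞ is left to extrapolation at T½ 4–8 h. The mildest case needs three conditions together, and the plan secures none of them. Half-life suffers only with multi-phase decline, assay noise or an unquantifiable 48 h sample; renal clearance only if it is computed over 0–24 h. Safety is unaffected.

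This should be fixed. The grounds are the low cost and the irrecoverable sample rather than the largest percentages.

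**What to change.** End the Cohort 3 list with 12:00, 24:00 and 48:00, as for Cohort 4, and make any other statement of the schedule agree. Otherwise state why 24:00 is left out. The cost is a one-line correction and one extra draw, with its paired storage sample, in six volunteers who are already in hospital.

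If Cohort 3 has already been sampled without it:

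- report AUC0-12 for all cohorts alongside the planned AUCs;
- compute renal clearance over 0–12 h in Cohort 3, and over the same window in every other cohort that is set beside it;
- flag Cohort 3's AUC0-∞ and half-life as less reliable.

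This fallback needs no new data.
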